6. PATIENTS	
7. TREATMENT AND SCHEDULE OF EVENTS	12
8. ADJUDICATION OF EVENTS	13
9. STATISTICAL ANALYSIS	13
10. DIRECT ACCESS TO SOURCE DATA/DOCUMENTS	14
11. QUALITY CONTROL AND QUALITY ASSURANCE	14
12. DATA HANDLING AND RECORD KEEPING	15
13. ETHICAL CONSIDERATION	16
APPENDIX I: ABBREVIATIONS AND ACRONYMS	16
APPENDIX II· REFERENCES	17

PROTOCOL SYNOPSIS

PROTOCOL TITLE: Italian National Registry on Bioresorbable Vascular Scaffold (ABSORB) for diffuse coronary disease

CLINICAL PHASE: IV

AIM OF THE STUDY: to investigate the procedural as well as the long-term clinical performance of the ABSORB technology in patients with an indication to percutaneous coronary intervention for: 1) multivessel disease (at least two significant stenosis in 2 different coronary arteries), or 2) long (>24 mm) single vessel disease.

PRIMARY ENDPOINT: the cumulative hierarchical incidence of major adverse cardiac events (MACE) defined as: cardiac death, non-fatal target vessel myocardial infarction (MI), or clinically driven target lesion revascularization (TLR).

SECONDARY ENDPOINTS: All causes mortality, clinically driven TLR, clinically driven target vessel revascularization (TVR), any revascularisation (non TLR, non TVR) and ARC-defined stent thrombosis, at any time point, any type of angina.

STUDY DESIGN: multicenter (50 to 80 centers across the Italian territory), prospective observational registry aiming to enroll a population of 1000 patients.

STUDY DURATION: We project 12 months for recruitment, 5 year follow-up duration after last patient in the registry.

CLINICAL FOLLOW-UP PLAN: 30 days, 6 months, 1 year, and then yearly up to 5 years after the index procedure.

PATIENTS SELECTION CRITERIA:

 Indication to percutaneous coronary intervention for multivessel disease or long (>24 mm) single vessel disease following:

ong (224 mm) single vessel disease Tollowing.

§ Stable angina or evidence of myocardial ischemia with stress

echocardiography/ myocardial SPECT/exercise test, or

§ Unstable angina / non ST-elevation myocardial infarction

§ ST-elevation myocardial infarction with de novo culprit lesion.

EXCLUSION CRITERIA:

Known intolerance to any of the device components

Contraindication to dual antiplatelet therapy (DAPT)

Lesion in a saphenous vein graft

Lesion to left internal mammary artery

Unprotected left main stenosis

Woman with childbearing potential

Age < 18y/o

Concomitant indication to open heart surgery

Inability to provide written informed consent

EFFICACY PARAMETERS: TLR and TVR up to 5-year follow-up.

SAFETY "PATIENT ORIENTED" PARAMETERS: all cause mortality, any myocardial infarction, Stent thrombosis based on the ARC classification, up to 5-year follow-up. Data on dual antiplatelet therapy use will also be collected and analyzed.

Sample size justification: Being this an observational registry aiming at quantifying effect estimates without direct comparisons to literature benchmarks, we relied on confidence interval profiling for sample size justification, without proceeding with formal power analysis. As the main analysis is a pooled analysis of patients with multivessel disease and/or long lesions, an overall and comprehensive analysis is planned as the primary analytical approach. Accordingly, we computed that a target

sample of 1000 patients will enable the computation of reasonably precise 95% confidence intervals. Specifically, assuming a 4.2% MACE rate at 1 year (in keeping with ABSORBD EXTEND data), confidence intervals computed with the adjusted Wald method would be 3.1% to 5.6% for a 1000-patient sample (point estimate 42/1000 [4.2%]).

Given that the registry aims to reflect real-world patients and practice, no provision to limit or restrict patient enrolment depending on the presence of multivessel disease vs long lesions is envisioned.

Analytical plan: Continuous variables will be reported as mean (standard deviation) and categorical variables as n (%). Survival analysis will be performed with the Kaplan-Meier method. Statistical inference will be based on the computation of overall 95% confidence intervals using the adjusted Wald method. Additional analyses will involve key subgroups defined according to baseline, lesion, and procedural features, with statistical significance set at the 5% 2-tailed level. Specifically, Student t, Fisher exact, and log-rank tests will be used for such bivariate analyses, whereas multivariable linear regression, logistic regression, and Cox proportional hazard analyses will be used to adjust for confounders. In addition, separate analyses for patients with only multivessel disease, patients with only long lesions, and patients with both conditions will be performed.

1. INTRODUCTION

The Italian National Registry on Bioresorbable Vascular Scaffold (ABSORB) for diffuse coronary disease is a investigator-initiated, single arm, prospective, multicenter post-market registry of patients with an indication to percutaneous coronary intervention for: 1) multivessel disease (at least two significant stenosis in 2 different coronary arteries), or 2) long (>38 mm) single vessel disease to de novo lesions treated with the Absorb Bioresorbable Vascular Scaffold (Absorb BVS, manufactured by Abbott Vascular) per IFU (on-label use). This Registry will enroll a minimum of 500 patients in approximately 50 sites throughout the Italian territory where Absorb BVS has regulatory approval and is commercially available.

2. BACKGROUND INFORMATION

2.1 Coronary device evolution

In 1977 Andreas Grüntzig performed the first balloon coronary angioplasty a revolutionary treatment that lead to the birth of a new specialty, "interventional cardiology".

Since that pioneering procedure, extensive developments and advances culminated in percutaneous coronary intervention (PCI) being 1 of the most frequently performed invasive medical procedures in clinical practice today.

Coronary stents, which were first developed in the mid- 1980s (1), have ultimately replaced "plain old balloon angioplasty" (POBA) as the preferred method of performing PCI, after the observed improvements in angiographic and clinical outcomes seen with their use (2,3).

Coronary stenting became widely implemented after the publication of the landmark BENESTENT trial (4) and the STRESS (5), together with evidence indicating that stenting was safe in the absence of anticoagulation therapy with the use of dual antiplatelet therapy (DAPT) (6-8) and/or adequate stent deployment (9).

By 1999, coronary stenting was performed in 84.2% of PCI procedures (10); however, despite their obvious advantages, there were associated problems and concerns. Most notably, and in addition to the risk of subacute thrombosis, an iatrogenic problem emerged in the form of in-stent neointimal hyperplasia (11-13). This intrastent growth of scar tissue, which was the result of proliferation and migration of vascular smooth muscle cells, and directly linked to stent implantation, resulted in restenosis rates of 20% to 30% (14). It was the attempts to minimize this in-stent neointimal hyperplasia, and thereby reduce rates of repeat revascularization, that ultimately lead to another revolution: the DES. The dramatic reduction in restenosis rates seen with the use of these DES compared with BMS (15-19) has been the major driving force behind the exponential growth of PCI as a treatment for patients with coronary artery disease (CAD). This increased confidence lead to a rapid and unprecedented uptake in their use, so that by 2005, 80% to 90% of all revascularization procedures in the U.S. were performed using a DES (20).

Even drug-eluting permanent metallic stents, however, have some short and long-term limitations: a still unclear duration of dual antiplatelet therapy which is strongly linked to the risk of stent thrombosis that, although infrequent, is a ominous event with poor prognosis; the preclusion of surgical revascularization; the jailing of side branches; the impairment of non-invasive imaging of coronary arteries with multislice computed tomography and magnetic resonance; the limitation of the ability of a treated segment to completely regain the functionality observed after balloon angioplasty.

2.2 Absorb BVS technology

The Absorb BVS System is a bioresorbable poly(L-lactide) (PLLA) scaffold with a drug and bioresorbable polymer coating [formulation of everolimus in a bioresorbable poly(D,L-lactide) (PDLLA) coating]. The transient nature of the Absorb BVS reduces the potential for late inflammation and thrombosis, which may subsequently reduce the need for long-term dual antiplatelet therapy (DAPT), permit late expansive remodeling of tissue and the return of natural vasomotion, as well as provides compatibility with a broader range of diagnostic imaging technologies.

The Absorb BVS System was granted Conformité Européenne (CE) Mark approval on December 14, 2010. The Abbott Vascular ABSORB Clinical Program currently has one completed clinical trial (ABSORB Cohort A), three on clinical follow-up (ABSORB Cohort B, ABSORB EXTEND, and ABSORB II RCT) and two that are actively enrolling (ABSORB FIRST and ABSORB III). To date, the ABSORB Cohort A, ABSORB Cohort B and ABSORB EXTEND clinical trials have provided acute and preliminary long-term data on the safety and performance of Absorb. ABSORB Cohort A and B also revealed preliminary evidence of vasomotion suggests natural vessel function.

ABSORB Cohort A/B.

The First in Man clinical investigation is a prospective, open-labeled, non-randomized, multi-center trial that was divided into ABSORB Cohort A Trial (n=30) and ABSORB Cohort B Trial (n=101). In the ABSORB Cohort A trial, among 29 patients, the 5-year MACE rate was 3.4%, due to only one ischemic MACE event (non-Q wave MI.) Additionally, there were no incidences of scaffold thrombosis or cardiac death out to 5 years. On Cohort B. design modifications to the device were made to improve the performance of Absorb. The materials are the same, and the drug (everolimus) release rate profiles are similar in both devices. The currently commercial Absorb BVS device is the same design as the Cohort B device. The ABSORB Cohort B trial had two subgroups (B1 and B2). 3-year follow-up data is available for Group B1 (n=45) and was recently reported at the ACC 2013 meeting. In the ABSORB Cohort B trial, among 100 patients f, the 3-year ischemic driven MACE rate was 10.0%- There has been no reported scaffold thrombosis.

ABSORB EXTEND

ABSORB EXTEND is a prospective, single-arm, open-label clinical study that is planned to enroll up to 1,000 subjects at up to 100 global sites. Clinical follow-up is being planned on all subjects enrolled in the trial for up to 3 years. Based on an interim data snapshot presented during PCR Rotterdam 2013 the first 450 patients have completed the 12-month follow-up. At 12-months, ischemic driven MACE rate was 4.20%. Scaffold thrombosis rate was 0.9%.

ABSORB II

ABSORB II is a pivotal ABSORB trial designed to demonstrate superiority Absorb compared to a commercially approved, active control stent, XIENCE PRIME. ABSORB II is a randomized, active-controlled, single-blinded, multicenter clinical trial and will enroll approximately 501 subjects in approximately 40 investigational sites in Europe. This trial will evaluate the following novel primary endpoints of vasomotion and change in lumen diameter. Enrollment has been completed on June 2013.

ABSORB III

The ABSORB Randomized Controlled Trial (RCT) is designed to evaluate the clinical safety and efficacy of Absorb for US approval. Absorb will be compared to the commercially approved, active control stent in the XIENCE family. The ABSORB III

is a prospective, randomized, active-control, single-blind, multi-center clinical trial that will register approximately 2,250 subjects in up to 220 sites in the US and outside the US. ABSORB III started at December 2012

ABSORB FIRST

The ABSORB FIRST Registry is a single arm, prospective, international post-market registry of patients with de novo lesions in previously untreated vessels. The ABSORB FIRST Registry will enroll a minimum of 10,000 patients in approximately 300 sites throughout multiple countries. ABSORB FIRST started at January 2013

While these results available were obtained in patients with relatively simple lesion complexity, the **Italian National Registry** is intended to provide an **independent assessment** of the safety and clinical outcomes of the Absorb BVS device in patients with multivessel/diffuse disease. Clinical effectiveness in smaller vessels, longer lesions and more complex type of lesions in patients with MDV and diffuse disease, with more frequent use of planned overlapping devices and at higher risk of coronary and cardiovascular events has not been demonstrated. Although implantation of DES in patients with MVD has become common practice, data about efficacy and safety of DES in this specific setting are scarce. Question regarding use of PCI vs CABG is this population is still opened. The availability of potential more effective devices as ABSORB could hypothetically improve the efficacy of PCI

2.2 Registry Device

The device to be used in this registry is the Absorb Bioresorbable Vascular Scaffold (Absorb BVS) System manufactured by Abbott Vascular. The Absorb BVS system refers to a system that consists of the Absorb BVS and a delivery system. Absorb BVS refers to the product in general (see the IFU for details concerning indications for use, contraindications, system preparation, precautions, and warnings).

3 REGISTRY OBJECTIVE

To investigate the procedural as well as the long-term clinical performance of the ABSORB technology in patients with an indication to percutaneous coronary intervention for:

- 1) multivessel disease (at least two significant stenosis in 2 different coronary arteries), or
- 2) long (>24 mm) single vessel disease.

4 REGISTRY FLOW AND CLINICAL FOLLOW-UP SCHEDULE

The Italian National Registry is a prospective multi-center nation-wide registry evaluating the safety and clinical outcomes of the Absorb BVS in daily use in patients with de novo lesions in previously untreated vessels with indication to PCI for multivessel or long single coronary artery disease.

Indications, however, are per the most recent Absorb IFU.

4.1 Number of Patients to be Registered and Patient Follow-up

The Italian National Registry will enroll a of 1000 patients in approximately 50 sites throughout the Italian territory where Absorb BVS has regulatory approval and is commercially available.

Patients will have clinical follow-up by telephone contact or office visits.

4.2 Measures Taken to Avoid and Minimize Bias

In order to minimize bias in assessing MACE outcomes, these events will be adjudicated by an independent committee.

4.3 Clinical follow-up plan: 30 days, 6 months, 1 year, and then yearly up to 5 years after the index procedure.

5. OUTCOMES/ENDPOINTS

Outcomes are as specified below:

- **5.1 Primary**: the cumulative hierarchical incidence of major adverse cardiac events (MACE) defined as: cardiac death, non-fatal target vessel myocardial infarction (MI), or clinically driven target lesion revascularization (TLR);
- **5.2 Secondary endpoints:** All causes mortality, clinically driven TLR, clinically driven target vessel revascularization (TVR), any revascularisation (non TLR, non TVR) and ARC-defined stent thrombosis, at any time point. Any type of angina post procedure measured by means of the Cardio Test, proposed by the ANMCO (Associazione Nazionale Medici Cardiologic Ospedalieri) [21]
- **5.3 Efficacy parameters**: TLR and TVR up to 5-year follow-up.
- **5.4 Safety "patient oriented" parameters:** all cause mortality, any myocardial infarction, Stent thrombosis based on the ARC classification, up to 5-year follow-up. Data on dual antiplatelet therapy use will also be collected and analyzed.

6. PATIENTS

6.1 Patient Population

Patients enrolled into this registry will be male and female patients derived from the general interventional cardiology population who satisfy the inclusion and exclusion criteria. The Italian National Registry will enroll 1000 patients in approximately 50 sites throughout the national terrritory (see section 4.1).

6.2 Patient Screening and Informed Consent

6.2.1 Patient Screening

All patients admitted for PCI should be evaluated for participation in the registry.

6.2.2 Informed Consent

The Investigator or designee, who has been trained on the protocol, will explain the nature and scope of the registry and inform the patient of the potential risks and benefits of participation, and document consent to treatment with an Absorb BVS device according to standard hospital practice. For this registry the patient must consent to data collection and follow-up visits. All patients (or legally authorized patients' representatives if applicable) must sign, date and time Medical Ethics Committee (MEC) approved informed consent prior to data collection for this registry. Obtaining the consent, provision of a copy to the patient, along with the date and time must be documented in the patient's medical records. The informed consent form must be signed by the investigator. In addition, the signed informed consent must be kept in the patient's medical records.

6.3 Eligibility Criteria

6.3.1 General Eligibility Criteria

Assessment for general eligibility criteria is based on medical records of the site and interview with a candidate patient. Patients must meet at least one of the angiographic inclusion criteria to be considered for the registry. If ANY of the exclusion criteria is met, the patient is excluded from the clinical evaluation and cannot be registered.

6.3.2 Inclusion Criteria

The inclusion criteria must follow the most recent IFU which may include but are not limited to the following:

- Patient must be at least 18 years of age at the time of signing the Informed
 Consent Form
- Patient is to be treated for de novo lesions located in previously untreated vessels.
- Patient must agree to undergo all required follow-up visits and data collection.
- Patient must have indication to percutaneous coronary intervention for multivessel disease (at least two significant stenoses in two different segments NOT as a bifurcation lesion) or long (>24 mm) single vessel disease following:
 - Stable angina or evidence of myocardial ischemia with stress echocardiography/ myocardial SPECT/exercise test, or
 - Unstable angina / non ST-elevation myocardial infarction
 - ST-elevation myocardial infarction with de novo culprit lesion.

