9.2 Analysis Population

All patients who are successfully registered will be included in the analysis. A limit of one third of the entire population will be set for the group of Multivessel Disease patients treated with ABSORB and a conventional stent ("hybrid group").

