9.4 Statistical Analyses

Continuous endpoints will be summarized by presenting the total number of patients, mean, standard deviation, median, minimum, and maximum. Tabulation of

categorical parameters will include counts and percentages. The outcomes will be summarized as both a discrete and a continuous variable using the method described above. Survival analysis will be performed with the Kaplan-Meier method. Statistical inference will be based on the computation of 95% confidence intervals using the adjusted Wald method. Additional analyses will involve key subgroups defined according to baseline, lesion, and procedural features, with statistical significance set at the 5% 2-tailed level. Specifically, Student t, Fisher exact, and logrank tests will be used for such bivariate analyses, whereas multivariable linear regression, logistic regression, and Cox proportional hazard analyses will be used to adjust for confounders. In addition, separate analyses for patients with only multivessel disease, patients with only long lesions, and patients with hybrid revascularization will be performed.

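### Section 6.3.2 defines multivessel disease by segments, while the synopsis aim, Section 1 and Section 3 define it by arteries, so the entry rule can admit patients outside both target populations

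*Protocol*

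**What the plan says.** Multivessel disease is defined in four places in the protocol.

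- Synopsis, aim of the study: "multivessel disease (at least two significant stenosis in 2 different coronary arteries), or 2) long (>24 mm) single vessel disease".
- Section 1: "multivessel disease (at least two significant stenosis in 2 different coronary arteries), or 2) long (>38 mm) single vessel disease".
- Section 3, the objective: "multivessel disease (at least two significant stenosis in 2 different coronary arteries), or", followed by the long single-vessel arm (>24 mm).
- Section 6.3.2, the inclusion criterion: "multivessel disease (at least two significant stenoses in two different segments NOT as a bifurcation lesion", followed by the same long single-vessel alternative (>24 mm).

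The synopsis selection criteria and Section 4 use the term multivessel without defining it.

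Three other provisions depend on the definition.

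- Section 6.3.1 makes one angiographic criterion sufficient: "Patients must meet at least one of the angiographic inclusion criteria to be considered for the registry". Section 9.2 then analyses every registered patient.
- Section 9.4 plans stratified results: "separate analyses for patients with only multivessel disease, patients with only long lesions, and patients with hybrid revascularization will be performed". The synopsis lists the same first two groups, but its third group is patients with both conditions.
- Section 9.2 caps the hybrid group, who also receive a conventional stent: "A limit of one third of the entire population will be set for the group of Multivessel Disease patients treated with ABSORB".

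**The concern.** Sites apply Section 6.3.2 when they enrol, while Section 3 states the question that the registry is meant to answer. If the entry rule is wider than the question, the pooled MACE rate covers some patients whom the objective does not describe. Section 9.3 makes that pooled analysis the primary one and sets no limit on the mix of multivessel and long-lesion patients, so nothing in the design bounds the share of such patients.

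The same uncertainty carries into the multivessel-only and long-lesion-only analyses and into the count for the hybrid cap. The synopsis foresees 50 to 80 centres, and centres that read the two wordings differently could enrol different patients under one protocol.

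**Working it through.** **The protocol's own figure.** Inputs from Section 9.3: 42 events in 1000 patients, adjusted Wald method, 95% confidence. With z = 1.96, z² = 3.84:

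- adjusted n = 1000 + 3.84 = 1003.84
- adjusted p = (42 + 1.92) / 1003.84 = 0.04375
- half-width = 1.96 × √(0.04375 × 0.95625 / 1003.84) = 0.01265
- interval = 3.11% to 5.64%

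This agrees with the stated 3.1% to 5.6%. The calculation does not use the multivessel definition, so the inconsistency leaves it unchanged. The definition matters only for whom the 4.2% is meant to describe.

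**The two definitions applied to patient types.** Lesion length is read per lesion, because Sections 9.3 and 9.4 speak of long lesions, and the >24 mm cut-off of Sections 3 and 6.3.2 is used.

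| Patient | Artery wording (synopsis aim, Sections 1 and 3) | Segment wording (6.3.2) |
|---|---|---|
| Separate stenoses in two arteries | Multivessel | Multivessel |
| One lesion >24 mm in one artery | Long lesion | Long lesion |
| Two separate, non-bifurcation stenoses in different segments of one artery, at least one >24 mm | Long lesion only | Both conditions |
| Two separate, non-bifurcation stenoses in different segments of one artery, each ≤24 mm | Neither arm | Multivessel |

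Rows 1 and 2 agree. In row 3 eligibility is the same but the stratum changes: long-lesion-only under one wording, both conditions under the other. In row 4 eligibility itself changes. Because Section 6.3.1 needs only one criterion, the segment wording is enough to let the row 4 patient in.

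**The hybrid cap.** One third of 1000 is about 333 patients. A patient with both lesions in one artery, treated with a scaffold and a conventional stent, counts towards that limit under the segment wording and not under the artery wording.

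**Size of the effect on MACE.** Let s be the share of one-artery patients in a stratum, p₂ the MACE rate in two-artery patients and p₁ the rate in one-artery patients. The reported rate is (1 − s)p₂ + s·p₁, so the shift is s(p₁ − p₂). The documents give none of s, p₁ or p₂; their only planning rate is the overall 4.2%. Neither the size nor the sign can therefore be computed. Purely to show scale, under assumptions not drawn from the documents: s of 15% to 30% and a difference of 4 percentage points give 0.15 × 4 = 0.6 to 0.30 × 4 = 1.2 points, in either direction.

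**The case against.** The narrower reading of 6.3.2 is available. The parenthesis qualifies the term multivessel, and the same sentence contrasts it with single-vessel disease. The bifurcation clause can be read as a restriction that stops one bifurcation from counting as two sites, not as an extension to one artery. Investigators trained on the protocol also see the artery wording in the aim and the objective. This stands as far as it goes: the text permits entry of one-artery patients but does not compel it. It does not remove the problem, because the parenthesis is worded as the definition and centres can reasonably differ.

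A reader might infer three stronger things.

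- *That one-artery patients will be analysed as multivessel.* The entry wording does not by itself fix the analysis stratum. Sections 9.4 and the synopsis name the strata without citing 6.3.2, and a statistical analysis plan that is not shown could define them by artery.
- *That these patients are at lower risk and dilute the MACE rate.* Nothing in the documents supports a direction.
- *That the registry could no longer attribute its MACE rate to multivessel or diffuse disease.* The title and Section 2 also speak of diffuse disease, and two stenoses along one artery are not clearly outside that wider question. The primary analysis is a descriptive pooled estimate without comparison to a benchmark. The supportable statement is narrower: such patients fit neither of the two populations named in Section 3.

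It can also be said that 6.3.2 deliberately broadened entry. The documents do not settle this. If it did, the objective is the text that needs changing.

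**Conclusion.** The point holds as an internal contradiction in an eligibility definition. Three places require two arteries, the inclusion criterion requires two segments, and nothing reconciles them. As worded, 6.3.2 can admit a patient with two lesions of 24 mm or less in one artery, who is in neither arm of the objective and might be counted as multivessel. The pooled population, the multivessel-only analysis and the hybrid cap are all exposed.

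How many patients are affected, and by how much MACE would move, cannot be computed from the documents. The planned confidence interval is unaffected. The conclusion assumes that the parenthesis in 6.3.2 serves as the definition and that lesion length is counted per lesion. The >38 mm cut-off in Section 1 is a separate inconsistency on which this conclusion does not rest.

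**What to change.** - Reconcile the synopsis aim, Sections 1, 3 and 6.3.2 to one definition. The artery wording matches the stated objective. If the segment wording is intended, change the aim, Section 1 and Section 3 instead, so that the objective names these patients.
- State that the chosen definition governs the multivessel-only analysis in Section 9.4 and the hybrid-group cap in Section 9.2.
- Derive multivessel status from the vessel recorded for each treated lesion. Section 7.1 leaves the baseline items to the eCRF, which is not shown, so confirm that vessel and lesion length are captured there.
- Keep patients already enrolled under the segment wording, but report those with lesions in only one artery outside the multivessel stratum.
- Add a sensitivity analysis of the pooled MACE rate that leaves out patients who meet neither arm of the objective.

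The cost is a short amendment, which under Section 13.1 needs ethics committee approval, plus one derived variable and one extra analysis. If the artery wording is adopted, slightly fewer patients may be eligible. Reclassification at analysis repairs the strata, but only the amended definition settles who belongs in the pooled primary population.
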